7.3. MODIFIED INTENT-TO-TREAT (M-ITT) POPULATION

The modified-Intent-to-Treat (m-ITT) Population will include all randomized subjects from the SAF who received at least one dose of study drug and have at least one VIIS assessment post visit 2. Subjects will be analyzed according to randomized treatment. Unless otherwise specified, efficacy analysis will be performed on this population.

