8.5. MISSING DATA

All available safety, PK and efficacy data will be included in data listings and tabulations. No imputation of missing data is planned for primary and secondary endpoints. Abnormal values for assessments (outliers) will be confirmed during the DRM and the primary analysis may be performed with and without inclusion of outliers.

IMPUTATION OF INCOMPLETE DATES.

An incomplete date is any date for which either the day, month or year is unknown, but all three fields are not unknown. An incomplete date occurs when the exact date an event occurred or ended cannot be obtained from a subject. For many of the analyses, a complete date is necessary in order to determine if the event should be included in the analysis (i.e., if the event is treatment-emergent) or to establish the duration of an event. In such cases, incomplete dates will be imputed.

For purposes of imputation, all events with an incomplete end date are assumed to have ended on or before the day the form was completed. In an effort to minimize bias, the project statistician will impute dates in a systematic, reasonable manner. A list of incomplete and imputed dates will be prepared by the project statistician or statistical programmer(s) and will be submitted for review by the clinical project manager and sponsor.

Syneos Health #1009367

Incomplete/missing start and stop dates will be handled as follows:

Table 8.4.1: Imputation of missing dates

Missing	Imputation
Start day	The start day will be imputed as the first day of the month with the following exception: if the partial date is the same month and year as the date of first dose of double-blind medication, then the partial date will be imputed as the date of first dose of double-blind.
End Day	The end day will be imputed as the last day $(28/29/30/31)$ of the month.
End Day and Month	d The end date will be imputed as the 31st of December or last day of study follow up.

For all other data, all available data will be included in the analyses and will be summarized as far as possible. Unless otherwise specified, there will be no substitution of missing data, i.e., missing data will not be replaced; missing data will be handled as 'missing' in the statistical evaluation.

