8.6. VISIT WINDOWS

The safety and efficacy data will be analyzed per study visit; the named visit as collected on the CRF will be displayed.

During the course of the study, blood draws and certain laboratory measurements for some subjects were delayed. A subset of subjects also experienced a 'treatment interruption' during which treatment was interrupted due to laboratory findings. Further detail will be provided in the Clinical Study Report. As a result, some study visits to occurred outside the pre-specified visit window. In the case where a scheduled study visit was delayed, the labelled study visit from the raw database will be used.

All unscheduled visit values will be excluded from summary tables but will be included on data listings.

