10.1. PRIMARY EFFICACY ENDPOINT AND ANALYSIS

The primary endpoint for the clinical trial is change from baseline in the VIIS scaling score in drug-treated subjects, as assessed by the investigator, in the target efficacy area. The VIIS provides five-point Likert scales (range 0-4) for erythema and scaling that increases in severity with increasing score values.

The target efficacy area for all efficacy analyses will be one of the body sites as defined in the VIIS tool (with the exception of Dorsal foot) with Grade 2 or higher on baseline VIIS scaling score as assessed by the Investigator.

The within-group change from baseline will be the primary focus of interest in the primary analysis.

Syneos Health #1009367

Primary Analysis

A Mixed Model Repeated Measures (MMRM) model will be used to perform the primary analysis of the VIIS scaling score in drug-treated subjects (not vehicle-treated subjects). Change from baseline VIIS scaling score will serve as the dependent variable. The model will include the baseline value (Visit 1) as a covariate (if useful) and visit (treated as a factor; the visit term will cover Visit 1, 5, 7, and 8). An unstructured covariance structure will be assumed and a Type III model will be evaluated. If the unstructured covariance structure matrix results in a lack of convergence, then Toeplitz (TOEP), first-order autoregressive (AR1), compound symmetric (CS) covariance structure will be used in that order. If the MMRM model cannot hit convergence with any correlation structure, then a within-subject t-test (baseline-adjusted, if useful) will be used to compare baseline to Visit 8. It should be noted that improvement will be signified by the existence of a negative change score.

The primary efficacy endpoint will be summarized descriptively by visit and across all visits. The table will contain descriptive statistics on observed values and change from baseline at each time point.

The primary analysis using the MMRM model will be summarized in a consolidated table containing the following:

- Descriptive statistics for change scores at baseline and each post-treatment time point.
- The LS mean change scores with accompanying standard errors and 95% confidence intervals for each visit.
- Within-group contrasts for each given visit.
- Significance levels for the visit effects.

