Along with the table detailing the results of the MMRM model, a consolidated table presenting the essential information for the primary analysis will be constructed. The primary endpoint will be deemed to have been met if the Visit 8 (week 24) term is significant, and the term coefficient is negative.

Secondary and Sensitivity Analyses Related to the Primary Outcome Variable

The following analyses will be performed to provide additional insight into VIIS scaling.

Responder Analysis

For drug-treated subjects, responder status will be assigned to a subject if at a given post treatment time point an improved change from baseline of at least 1 VIIS scaling

Syneos Health #1009367

unit occurs. A Generalized Estimating Equation (GEE) model will be used to evaluate the predicted log odds, odds and probability of response. The model will include the effect of visit (treated as a factor). An unstructured covariance structure will be assumed and a Type III model will be evaluated. If the unstructured covariance structure matrix results in a lack of convergence, then first-order autoregressive (AR1) and compound symmetric (CS) covariance structure will be used in that order.

Results will be captured in a consolidated table that contains the following information:

- Number and percent of observed responders and non-responders at all post-treatment time points;
- Significance levels for the visit effects;
- The model predicted log odds, odds and probability of response with standard errors and 95% confidence intervals for each visit;
- Within-group contrasts expressed as an odds ratio, accompanied by a 95% confidence interval.

AUC Analysis

For drug-treated subjects, AUC for change from baseline over all post-treatment time points will be calculated for each subject using the trapezoidal rule. A linear model comparing AUC to zero (no change from baseline) will be performed.

Survival Analysis

For drug-treated subjects, time to first response (i.e., a one-unit VIIS scaling improvement) will be captured in a Kaplan Meier plot. A hazard rate estimate will be generated.

Analysis for Patients Experiencing one or more Treatment interruptions

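### The secondary AUC analysis uses a raw area with no standardisation for time, so an early leaver without an early-termination value scores smaller than a completer with the same change

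*SAP*

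**What the plan says.** SAP 10.1, AUC Analysis, restricted to drug-treated subjects: "AUC for change from baseline over all post-treatment time points will be calculated for each subject using the trapezoidal rule". Then: "A linear model comparing AUC to zero (no change from baseline) will be performed". Item 2 of the SAP 10 overview describes the same analysis. Table 10.2.2 extends it to Investigator erythema and to central-reader scaling and erythema. Neither document gives a divisor, a fixed interval, a start point, or a choice between actual dates and scheduled weeks.

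The rules that decide which data enter the area are these:

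- SAP 8.5: "No imputation of missing data is planned for primary and secondary endpoints".
- SAP 7.3: a dosed subject is in the m-ITT population if they "have at least one VIIS assessment post visit 2".
- SAP 10.1, for the primary model: "the visit term will cover Visit 1, 5, 7, and 8". These visits are Day 1 and Weeks 12, 20 and 24.
- SAP 8.6: "A subset of subjects also experienced a 'treatment interruption' during which treatment was interrupted due to laboratory findings". On late visits it adds: "In the case where a scheduled study visit was delayed, the labelled study visit from the raw database will be used".
- Protocol Table 1 (footnote 2) and section 4.3 ask early leavers, where possible, for the Week 24 assessments. The schedule column is headed as both early termination (ET) and Visit 8. Neither document says at what time such a value enters the AUC.

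**The concern.** A trapezoidal area is change accumulated over time. If follow-up differs between subjects and nothing standardises for it, equal responses give unequal areas. Under the SAP's rules, a subject whose only later VIIS is at Week 12 contributes a 12-week area, and it is averaged with 24-week areas.

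At stake are the size of the mean AUC, the comparability of subjects within a group of about six, and some power. Because the time axis and the placement of ET values are not stated, two programmers could also compute different areas from the same data.

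**Working it through.** **The plan's own figure.** The documents give no figure for the AUC. The protocol's only power calculation (section 10.1) is a two-sided one-sample t-test with 20 active subjects, change -0.5 and alpha 0.05. The noncentrality is 0.5/0.6 x √20 = 3.73 for SD 0.6 and 0.5/0.7 x √20 = 3.19 for SD 0.7. Exact power is 94.2% and 85.8%, consistent with the stated 94% and 85%.

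**Inputs.** VIIS at Weeks 0, 12, 20 and 24 (SAP 10.1, Table 4.1.1); 6 treated subjects (Protocol synopsis); change -0.5 and SD 0.6 (Protocol 10.1). VIIS is also taken on Day 2. With no change by then, including it moves a completer's area only from -9.0 to -8.96.

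**Area by length of follow-up.** A = Σ (y_i + y_(i-1))/2 x (t_i - t_(i-1)), with y = 0 at Week 0, a constant change from Week 12, and no ET value.

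| Last VIIS | Change -1 | Change -0.5 |
|---|---|---|
| Week 24 | -6 - 8 - 4 = -18 | -9 |
| Week 20 | -6 - 8 = -14 | -7 |
| Week 12 | -6 | -3 |

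A Week 12 leaver with a change of -1 (area -6) ranks below a completer with half that change (area -9). With five completers and one Week 12 leaver, all at -1, the mean is (5 x -18 - 6)/6 = -16, which is 2/18 = 11% smaller.

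**Test against zero.** This was simulated with 40,000 trials per setting. The assumptions not in the documents are normal change scores, correlation 0.5 between visits, and random dropout of 0, 17 or 33% split between leaving after Week 12 and after Week 20.

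- No true change, n = 6: the raw AUC rejects in 4.5 to 5.1% of trials.
- Change -0.5, n = 6, 17% dropout: power 46% raw and 47% divided by observed time.
- Change -0.5, n = 6, 33% dropout: power 43% raw and 47% divided by observed time. The mean raw AUC falls from -9.0 to -7.7.
- Complete data, n = 6: power 49 to 50%.

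**Delayed visits, change -0.5.** On scheduled weeks the area is -9.0 whatever the delay. On actual dates, Visits 7 and 8 both six weeks late (assumed) give -3 - 7 - 2 = -12.0, and twelve weeks late gives -3 - 10 - 2 = -15.0.

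**Early-termination value, change -0.5.** An ET visit at Week 14 (assumed) recorded as Visit 8 gives -3 - 6 = -9.0 on scheduled weeks and -3 - 1 = -4.0 on actual time.

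**Dividing by observed time, change -1.** -18/24 = -0.75, -14/20 = -0.70, -6/12 = -0.50. The ratio of completer to Week 12 leaver drops from 3.0 to 1.5 but does not reach 1, because the ramp from baseline to Week 12 fills more of a short follow-up.

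**Fixed-interval contrast.** Over Weeks 0 to 24 the trapezoids are 6·W12 + 4·(W12 + W20) + 2·(W20 + W24) = 10·W12 + 6·W20 + 2·W24. Divided by 24, a change of -1 held from Week 12 gives -18/24 = -0.75.

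**The case against.** - **The area does measure effect.** A reader might infer that the AUC reflects time observed rather than response. It is response times duration: zero change gives zero area at any length of follow-up. The only planned test is against zero, and it keeps its level when dropout is unrelated to outcome. This objection stands.
- **Delays are handled by label.** Since SAP 8.6 reports interruptions and late visits, a reader might infer that those delays distort the AUC. The documents do not support this. SAP 8.4 defines the study visit as the nominal one, and 8.6 uses the visit label when a visit is late. On scheduled weeks a delay changes nothing. What remains is that the AUC text names no axis.
- **Early leavers may have an ET value.** If it is recorded as Visit 8 and placed at Week 24, the subject gets a full-length area. The fault would then be a misplaced value, not a short follow-up. The short area needs a leaver without an ET VIIS, and the documents report none.
- **Units.** The SAP compares the AUC only with zero, so unit-weeks break no stated threshold. A time-averaged value is in VIIS units but is still not a Week 24 change: -1 held from Week 12 averages -0.75.
- **Stakes.** This is one of several supporting analyses in Part 1. The SAP's success criterion is the Visit 8 term of the MMRM, and the protocol reserves the efficacy claim for Part 2. This limits the importance of the point but does not remove it.

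**Conclusion.** The point holds as a minor one. The planned AUC has no standardisation for time, and the missing-data and m-ITT rules let partial follow-up in. An early leaver without an ET value therefore gets an area as small as one third of a completer's for the same change.

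One such subject in six shrinks the mean by 11%. At an assumed 33% random dropout, power falls from about 50% to 43%. These figures rest on a constant change from Week 12 and on the assumed dropout rate, correlation and normality. If dropout depends on outcome, neither the error rate nor the size of the shrinkage is covered by this check.

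The time axis and the placement of ET values are unstated and should be settled. The documents do not show that delays have distorted the AUC, that false positives are inflated, or that the AUC definition affects the primary Visit 8 test.

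**What to change.** Replace the raw area with the time-averaged change over a fixed Week 0 to 24 interval on scheduled weeks. Take it as a contrast of the planned MMRM visit estimates, (10 x Week 12 + 6 x Week 20 + 2 x Week 24)/24, and test it against zero. This uses partial follow-up without imputation and reports in VIIS units. State the time axis and the start point. Place an ET value at the time it was taken, so that it does not count as Week 24 merely because of its label.

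The costs are:

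- A few more SAP lines, covering each endpoint given an AUC analysis.
- Reliance on the MMRM missing-at-random assumption.
- The contrast needs a converged MMRM. If the SAP's t-test fallback is used, another rule is required.
- If the contrast is read from the primary fit, the ET rule must be settled for that model too.

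The contrast's power at n = 6 was not computed here.

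A simpler alternative is to divide each subject's AUC by observed time. That is a partial remedy: it recovers about half of the lost power in the 33% dropout case (43% to 47%) but still gives -0.75 against -0.50 for the same response.

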The impact of Treatment interruptions on the primary outcome will be evaluated through sensitivity analysis. Patients with a treatment interruption of more than 1 week will be flagged. The same MMRM model of the primary analysis will be conducted on the ITT population with the treatment interruption as a categorical variable and the treatment interruption by treatment interaction as an additional independent variable. The analysis outcome will be summarized in the similar way as the primary analysis. Estimates of the treatment interruption effect variable will also be tabulated.

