10.4. EXPLORATORY ANALYSES

Efficacy Endpoint

Additional exploratory analysis maybe conducted on primary efficacy endpoint by sponsor. Exploratory analysis will be conducted for both targeted efficacy area and for combined regions as appropriate, such as but not limit to:

- 1) Repeat primary analysis MMRM model on drug-treatment patients to evaluate change from baseline for combined visits (Visit 5, Visit 7 and Visit 8)
- 2) Repeat primary analysis MMRM model on all treated patients (including both drug-treatment and vehicle-treated patients) to evaluate change from baseline for combined visits (Visit 5, Visit 7 and Visit 8) and each individual visit
- 3) all patients (including both drug-treatment and vehicle treated patients)
- 4) Responder analysis for patient with at least 2 units VIIS scaling improvement from baseline at any post treatment time point
- 5) Survival analysis for the time to first response defined as 2 units VIIS scaling improvement from baseline
- 6) AUC analysis for change from baseline of all VIIS regions combined
- Analyze change from baseline of VIIS total score at week 24 analysis using MMRM model
- 8) Contralateral analysis of between group contrast comparing VIIS scaling score change from baseline between treated area vs. untreated area
- 9) To further evaluate the impact of 'treatment interruption' on treatment effect, the same analysis approach used for primary analysis on primary endpoint may be repeated on following subgroups:
 - a. patient with 'treatment interruption' for at least 1 week

Syneos Health #1009367

b. patient without 'treatment interruption' or with 'treatment interruption' for less than 1 week

Biomarker Endpoint

Selected skin lipid bio markers, captured as the post-treatment value at Week 24 or at an early termination visit as the post-treatment minus baseline value (change score), may be correlated with various outcome symptom scales or functions of outcome symptom scales. Such skin lipid biomarkers are listed in Table 10.3.1.

Exploratory analyses will be performed on lipid biomarkers from skin cell analysis and TEWL using the following methodologies:

Analysis between biomarkers and outcome scales (investigator and central reader VIIS scaling and erythema) for time matched assessments will be performed using appropriate correlation procedures.

Table 10.3.1: Lipid Values Selected for correlational analysis (captured as post treatment values or change score values)

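### The interruption sensitivity analysis in SAP 10.1 tabulates one effect averaged over visits, not the effect at Visit 8, because the patient-level flag has no flag-by-visit term

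*SAP*

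**What the plan says.** SAP 8.6 reports what prompted the analysis: "A subset of subjects also experienced a 'treatment interruption' during which treatment was interrupted due to laboratory findings". SAP 9.2.1 adds that many of these subjects still received the whole course once study drug was restarted, and it subtracts interruption days from exposure.

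SAP 10.1 then sets out to evaluate the impact of interruptions on the primary outcome. "Patients with a treatment interruption of more than 1 week will be flagged". The model is given as "The same MMRM model of the primary analysis will be conducted on the ITT population with the treatment interruption as a categorical variable", with a flag-by-treatment interaction as a further term. For output, "Estimates of the treatment interruption effect variable will also be tabulated", alongside a summary like that of the primary analysis.

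The model being reused is restricted to drug-treated subjects. It has visit as a factor, and "the visit term will cover Visit 1, 5, 7, and 8". Its first-choice covariance is unstructured, followed by Toeplitz, AR(1) and compound symmetry. SAP 10.1 judges the primary endpoint on the Visit 8 (Week 24) term.

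SAP 10.4 item 9 allows, but does not require, the primary analysis to be repeated in two subgroups. One is defined as "patient with 'treatment interruption' for at least 1 week", the other as its complement. A one-week interruption is thus counted in 10.4 but not in 10.1.

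**The concern.** The flag belongs to the patient and does not change between visits. One interaction is named (with treatment) and it is not with visit. The model therefore forces the same flagged-minus-unflagged gap at Visits 5, 7 and 8, and the tabulated estimate is a weighted average of the visit-specific gaps. If an interruption began after Visit 5 or Visit 7, some of those visits were scored before it could have had any effect.

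The stated question is the impact on an endpoint judged at Visit 8. A single averaged coefficient does not answer it. It can understate a loss at Visit 8. It can show a loss at Visit 8 that has already recovered. It also reports as an interruption effect any chance difference already present at Visit 5. The by-visit least-squares means do not help, because the additive flag shifts them all by the same amount.

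**Working it through.** **Plan's own figure.** None: neither document states the size of an interruption effect, the number of subjects interrupted, or when interruptions began.

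**Inputs from the documents.** Post-baseline visits in the model: 5, 7 and 8, with Visit 1 also listed (SAP 10.1). Drug-treated subjects: 6 (Protocol synopsis, Statistical Analysis). Planning SD: 0.6 (Protocol 10.1, set for the Phase 2 scaling score).

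**Assumptions.** Complete data; no baseline covariate; drug-treated subjects only, with the flag-by-treatment term dropped because it cannot be estimated there; start times in one of three intervals; an effect that, once begun, is constant through Visit 8.

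**Formula.** For y(ij) = visit(j) + b × flag(i) with covariance V, the expected flag coefficient is b = Σ w(j) d(j). Here w = V⁻¹1 / (1ᵀV⁻¹1), and d(j) is the true gap at visit j as a fraction of the gap at Visit 8. So d is (1,1,1) for a start before Visit 5, (0,1,1) for a start between Visits 5 and 7, and (0,0,1) for a start between Visits 7 and 8.

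**Weights, three visits, equal variances.**
- Compound symmetry: 1/3 each.
- AR(1): end visits 1/(3 − ρ), middle visit (1 − ρ)/(3 − ρ). For ρ = 0.5 this is 0.40, 0.20, 0.40. For ρ = 0.8 it is 0.455, 0.091, 0.455.

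**Estimate as a fraction of the true Visit 8 effect.**

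| Covariance and visits | Start before Visit 5 | Visits 5 to 7 | Visits 7 to 8 |
|---|---|---|---|
| Compound symmetry, 3 visits | 1.00 | 0.67 | 0.33 |
| AR(1) ρ 0.5, 3 visits | 1.00 | 0.60 | 0.40 |
| AR(1) ρ 0.8, 3 visits | 1.00 | 0.55 | 0.45 |
| Compound symmetry, Visit 1 included | 0.75 | 0.50 | 0.25 |
| AR(1) ρ 0.5, Visit 1 included | 0.67 | 0.50 | 0.33 |
| Unstructured, SDs 0.4/0.6/0.8, correlation 0.5 | 1.00 | 0.12 | −0.04 |
| Unstructured, SDs 0.8/0.6/0.4, correlation 0.5 | 1.00 | 1.04 | 0.88 |

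The unstructured SDs are assumed. The Visit 1 rows are illustrative, since change at Visit 1 is zero by definition and equal variance cannot hold there. As an example of the three-visit rows, a true loss of 0.5 grade at Visit 8 would be tabulated as 0.27-0.33 for a start between Visits 5 and 7 (0.5 × 0.545 to 0.5 × 0.667). For a start between Visits 7 and 8 it would be 0.17-0.23 (0.5 × 0.333 to 0.5 × 0.455).

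**If the effect has gone by Visit 8.** Take a start between Visits 5 and 7 with recovery, so that the gap exists only at Visit 7. The coefficient is then 0.33 (compound symmetry), 0.20 (AR(1), 0.5) or 0.09 (AR(1), 0.8) of the Visit 7 gap, although the true Visit 8 effect is zero.

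**Simulation check.** 4,000 subjects, half flagged, compound symmetry, three visits, true effect 0.5. For the three timings in order, estimate/true was:
- flag as written: 1.02, 0.68, 0.33;
- flag-by-visit, read at Visit 8: 0.98, 1.00, 0.96.

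**Precision.** Six subjects split 3/3, SD 0.6, correlation 0.5. Averaged flag: variance 0.36 × (1 + 2 × 0.5)/3 × (1/3 + 1/3) = 0.16, SE 0.40. Visit 8 alone: 0.36 × (1/3 + 1/3) = 0.24, SE 0.49. With a 1/5 split these become 0.54 and 0.66.

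**The case against.** The strongest reply is that timing is unknown. SAP 8.6 refers only to a subset of subjects. A reader might infer from the safety-blood schedule (Weeks 12, 20 and 24 in Protocol Table 1) that many interruptions began after the Week 12 score. The documents do not support that inference: the SAP schedule also marks Week 4 bloods, SAP 8.6 says draws were delayed, and unscheduled visits are recognised. An interruption before Visit 5 causes no dilution over the post-baseline visits. Persistence is also unknown, since many subjects completed the full course after restarting. These points stand, and they make any single shrinkage figure conditional.

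Second, SAP 10.4 item 9 could already supply a Visit 8 estimate in each subgroup. That is true, but it is optional, exploratory and uses a different threshold, so it does not commit the sponsor to one.

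Third, a patient-level flag is adequate at Visit 8 itself, because an on-treatment interruption precedes that score. This also stands. The gap is the missing visit interaction, and recoding the flag visit by visit is not needed.

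Fourth, with about six drug-treated subjects the distortion is under one standard error: in the 0.5-grade example at most 0.5 − 0.17 = 0.33, against 0.40. That limits the practical weight of the point. It does not make an averaged coefficient the right summary of Week 24.

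**Conclusion.** The point holds as a mismatch between the analysis and its own question: SAP 10.1 asks about an endpoint judged at Visit 8 and tabulates an effect averaged over visits. The three-visit factors of 1.00, 0.55-0.67 and 0.33-0.45 rest on equal variances, persistence to Visit 8, and compound symmetry or AR(1) with correlation 0.5-0.8.

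A reader might infer that the estimate generally shrinks to between one third and two thirds of the truth. The documents do not support that. The factor depends on start times they do not give, on whether Visit 1 enters, and on a covariance whose first choice is unstructured, where the illustrative values ran from −0.04 to 1.04. Nor is the error always toward zero, as the recovery case shows. Nor is the primary result at risk: the coding of this flag does not touch the primary Visit 8 test.

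**What to change.** In SAP 10.1, add a flag-by-visit term to the interruption model. If too few subjects are flagged to fit it, compare flagged and unflagged subjects at Visit 8 alone. Name the Visit 8 estimate, with its 95% confidence interval, as the sensitivity result. Use one duration threshold in 10.1 and 10.4 item 9.

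While editing the paragraph, settle which subjects are in the model. The flag-by-treatment term cannot be estimated among drug-treated subjects only, and the paragraph names an ITT population where SAP 7.3 defines a modified one.

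The cost is SAP wording and one model term. Precision falls from an SE of about 0.40 to about 0.49 grade (SD 0.6, 3/3 split), so the interval will be wide and should be reported as such. A wide interval must not be read as evidence that interruptions had no effect.
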